## 2. Glossary

[figure not shown]
9-HPT	9-Hole Peg Test
AE	Adverse Event
AR	Adverse Reaction
BBB	Blood Brain Barrier
CD	Cluster Differentiation
CI	Chief Investigator
Clad	Cladribine
CRF	Case Report Form
CSF	Cerebrospinal Fluid
CXCL-13	Chemokine-13
EDSS	Expanded Disability Status Scale
FACS	Fluorescence-activated cell sorting
FBC	Full blood count
FLC	Free Light Chains
GAP-43	Growth Associated Protein-43
GFAP	Glial Fibrillary Acidic Protein
IgG	Immunoglobulin G
JRMO	Joint Research Management Office
LFT	Liver Function Test
MSFC	Multiple Sclerosis Functional Composite
MSIS-29	Multiple Sclerosis Impact Scale-29
NCAM	Neural Cell Adhesion Molecule
NEDA	No Evidence of Disease Activity
NF	Neurofilament
OCB	Oligoclonal Bands
PROMS	Patient reported outcome measures
PBMC	Peripheral Blood Mononuclear Cells
REC	Research Ethics Committee
RRMS	Relapsing Remitting Multiple Sclerosis
SAE	Serious Adverse Event
SAP	Statistical analysis plan
SAR	Serious Adverse Reaction
SDMT	Single Digit Modalities Test
SOP	Standard Operating Procedure
SUSAR	Suspected Unexpected Serious Adverse Reaction
T25FW	Timed 25 Foot Walk
U&E	Urea & Electrolytes
WCC	White Cell Count

## 4. Summary and synopsis

Short title	Clad-B Study
Methodology	Longitudinal study
Research sites	Barts Health NHS Trust Queen Mary, University of London
Objectives / aims	
Primary: To quantify the temporal changes of memory B cells (CD19+/CD27+/IgD-+), plasmablasts (CD19-/CD138+/CD38+) and T cells (CD4/CD45RA-/, CCR7-/, CD8+/CD45RA-+/CCR7-+), Tregs (CD4/CD8)/CD25+/CD127-/Fox3 P+) in the peripheral venous blood of pwMS with RRMS over 96w of treatment with oral cladribine.
 
These will be compared to the populations of non-memory or class-switched B cells (immature/transitional B cells CD10+/CD38+/CD19+, immature regulatory B cells CD10+/CD38+/CD19+/CD24+/IL-10+, mature B cells CD10-/CD38+/CD19+).
 
Secondary:
 
 
1. To study the effects of oral cladribine on: 
 
a. CSF OCBs and free immunoglobulin kappa and lambda light chain levels (FLC).
 
b. CSF markers of inflammation, in particular CXCL-13 and urine markers of inflammation (neopterin).
 
c. CSF markers of neuroaxonal damage, in particular free neurofilament light chains.
 
d. On the peripheral repertoire B-cells (immunoglobulin) and T-cells (T cell receptor) and plasma cells (soluble receptors).
 
 
 
2. To compare CSF OCB positivity and CSF light chain levels with a contemporary control group of alemtuzumab treated pwMS (historical data).
 
 
Tertiary:
 
 
1. To compare B and T cell repertoire with a contemporary control group of alemtuzumab treated pwMS (historical data).
 
2. To evaluate the effect of changes in the immune cell profile on clinical measures of disability, MRI activity and PROMS.
 

Number of participants	13
Inclusion and exclusion criteria	
Inclusion:
 
 
• Patients with RRMS who are being treated with oral cladribine at Barts Health NHS Trust
 

	
 
• Patients must be willing and able to undergo lumbar punctures
 
• Patients who are OCB positive in their CSF (from previous diagnostic lumbar puncture)
 
 
Exclusion:
 
 
• Ineligible for oral cladribine under NHS England prescribing guidelines and those participating in MAGNIFY-MS study (cladribine tablets in active MS)
 
• Unsuitable to have a lumbar puncture (e.g. spinal deformity, tethered cord syndrome, or the use of aspirin or anticoagulants), and those unable to comply with study requirements, including frequency of visits and lumbar punctures
 
• Presence of comorbidities in which administration of cladribine is contraindicated
 
• Abnormal baseline investigations (WCC<3 x 10^9/l, neutrophil count < 1.5 x 10^9/l, platelet count < 100 x 10^9/l, haemoglobin < 110 g/l, LFT >/= 3x upper limit of normal site reference ranges, potassium < 2.8 mmol/l or > 5.5 mmol/l, sodium < 125 mmol/l, creatinine > 130 umol/l
 

Statistical methodology and analysis (if applicable)	
Changes in total immune cell counts will be analysed using descriptive statistics, including reduction relative to baseline and absolute reduction in numbers. Time to nadir and recovery will be done using best-fit modelling.
 
Total blood IgG and free kappa and lambda light chain levels will be normalised to albumin levels. McNemar's test will be used to compare differences in OCB status between baseline, year one or year two. The association between different biomarkers, clinical and imaging parameters will be analysed using multiple regression.

Study duration	96 weeks.

## 5. Introduction

There is emerging data that suggests that B cells, in particular memory B cells, and intrathecal plasma cell responses in multiple sclerosis (MS) are pathogenic and the intrathecal component is one of the proposed mechanisms that drives delayed non-relapsing progressive MS. As cladribine penetrates the central nervous system, and might have activity against both B-cells and plasma cells, we hypothesise that cladribine may be superior to other disease-modifying therapies by targeting pathogenic intrathecal B-cells and plasma cells. We are particularly interested in see if cladribine targets the intrathecal long-lived plasma cells and the oligoclonal IgG bands (OCBs) they produce, since OCBs have, to date, proven resistant to current treatments including high efficacy treatments such as alemtuzumab. In addition, we will study the effect of cladribine on intrathecal inflammatory (CXCL13) and neurodegenerative (neurofilament light chain) markers. As recent evidence supports the hypothesis that cladribine is working via memory B cells, we will therefore assess the impact of oral cladribine on the kinetics of different peripheral B and T cell depletion and repopulation rates. Finally we will assess the impact of oral cladribine on both the B-cell (immunoglobulin) and T-cell (T cell receptor) repertoire.

observation was not confirmed in a larger, more definitive, German study (Harrer et al. 2013). It is important to note that in pwMS treated with alemtuzumab intrathecal oligoclonal bands persist (Hill-Cawthorne et al. 2012). In comparison, in the Scripps chronic progressive cladribine trial, patients treated with cladribine had a significant decline in the number of oligoclonal bands (Sipe et al. 1994). Although the OCBs did not disappear this study used agarose gel electrophoresis, a technique that is not specific for detecting immunoglobulins and is now obsolete (Freedman et al. 2005).

We hypothesise that it will be important to target intrathecal plasma cells therapeutically to delay the onset, or slow down, the clinically-apparent progressive phase of MS. Most licensed DMTs are effective, to a greater or lesser extent, at suppressing relapses and focal MRI activity (new T2 or Gd-enhancing lesions), however, none of the treatments have yet been shown to prevent the onset of non-relapsing progressive disease. Why? If the non-relapsing progressive phase of the disease is driven by intrathecal OCBs, the resistance of long-lived plasma cells to current therapeutic intervention may explain why this phase of the disease is so resistant to treatment. To successfully treat, or prevent, progressive MS intrathecal plasma cells may need to be eliminated to prevent antibody mediated mechanisms that underlie the progressive phase of MS. We are thus actively exploring treatments that target intrathecal plasma cells; for example, we are proposing that cladribine (2-chlorodeoxyadenosine) a nucleoside analogue penetrates the blood-brain barrier (BBB) and has been shown to have biological activity against myeloma cells, or malignant plasma cells, albeit in combination with a STAT3 inhibitor (Ma et al. 2011).

This suggests that cladribine may target both peripheral and central anti-inflammatory mechanisms including pathogenic intrathecal plasma cells. We hypothesise therefore that cladribine will be effective as a treatment for progressive MS; cladribine by targeting intrathecal plasma cells in MS will reduce intrathecal IgG and free light chain production and may result in the disappearance of intrathecal OCBs. We are therefore proposing an intensive B-cell biomarker study (CLAD-B study) to explore the effect of cladribine on peripheral and intrathecal B cells and plasma cells. As cladribine has a greater impact on peripheral B cells, in particularly memory B cells (B. Ceronie, M. Zhifeng, F. Ammoscato, H. Lock, H.J. Longhurst, G. Giovannoni, D. Baker, K. Schmierer 2017), and to look at the differential effect of cladribine on both the T & B cell repertoire.

We have recently hypothesised that all effective MS DMTs, particularly high-efficacy DMTs, work via targeting the peripheral memory B-cell population and suggested that cladribine may be preferentially working as semi-selective B-cell agent (Baker et al. 2017). We now have cross-sectional pilot data from patients treated with parenteral cladribine showing prolonged peripheral memory B-cell depletion of a similar magnitude to alemtuzumab-treated patients (Baker et al. 2017; B. Ceronie, M. Zhifeng, F. Ammoscato, H. Lock, H.J. Longhurst, G. Giovannoni, D. Baker, K. Schmierer 2017). As part of this study we propose defining in detail the changes in peripheral lymphocyte subsets in both the depletion and repopulation phases after oral cladribine. In addition, we will study the effects of oral cladribine on the peripheral blood B and T cell repertoire by studying the immunoglobulin and T-cell receptor diversity.

## 5.2 Preclinical data

### Intrathecal plasma cell and B cell biology

In MS both quantitative and qualitative assays are used to assess pathological intrathecal IgG production, which is an indicator of intrathecal B cell and plasma cells activity. From a diagnostic perspective qualitative assays are more sensitive being abnormal in 95-98% of patients with clinically definite MS. The Ig-Index, and other similar indices, are less sensitive only being abnormal in ~70% of people clinically-definite MS. However, these indices do provide a proxy of the intrathecal B and plasma cell activity. The downside of using IgG as a marker of activity is its long circulating peripheral half-life of IgG that results in the equilibration of levels between the blood and intrathecal compartments. The equilibration ratio is very sensitive to any disruptions in blood-brain-barrier (BBB) hence the need to adjust CSF:plasma IgG ratio with the albumin quotient, an index of BBB integrity. In comparison free immunoglobulin light chains (FLCs), both kappa and lambda, have a very short circulating half-life due to their high fractional excretion rate in the kidney and catabolism. As a result levels of FLCs between the blood and CSF don't equilibrate. Therefore, CSF FLC levels are a very good proxy of intrathecal B-cell and plasma cell activity. Therefore, any drug that reduces activity of B-cells and/or plasma cells will lower FLC levels. Unfortunately, FLCs don't differentiate between B-cells and plasma cells. We are not aware of any specific soluble CSF biomarker, apart from FACs analysis of free cells in the CSF that can reliably differentiate between B-cells and plasma cells.

The molecular mechanisms underlying terminal differentiation of B cells into plasma cells, and long-lived plasma cells, are partially understood and involve both transcriptional and epigenomic changes. As B cells differentiate into plasmablasts there is a committal step in which an S phase-synchronized differentiation switch is associated with an extensive DNA demethylation and local acquisition of 5-hydroxymethylcytosine at enhancers and genes related to plasma cell identity (Caron et al. 2015). Downregulation of both TGFb1/SMAD3 signaling and p53 pathway support this final step, allowing the emergence of a CD23-negative subpopulation in transition from B cells to plasma cells. Hydroxymethylation of PRDM1, a gene essential for plasma cell fate, is coupled to progression in S phase. DNA methylation patterns can potentially be used to study the B cell maturation process in the context of MS (Kulis et al. 2015) and we propose exploratory epigenetic studies in the future (samples from this study will be stored for this).

### B-cells

Preliminary evidence from therapeutic studies suggests that the memory B cell pool might play a crucial role in the disease pathogenesis (Baker, D., Marta, M., Pryce, G., Giovannoni, G., Schmierer, K. 2016). Limited evidence has shown that the memory B cell pool is suppressed by several of the disease modifying therapy (DMT) agents used in RRMS (Kasper et al. 2014)(Thompson et al. 2010)(Rieckmann 2009; Palanichamy et al. 2014). This appears to correlate with disease suppression and the desired clinical outcome of no evidence of disease activity (NEDA)(Coles et al. 2012; Leist et al. 2014; Bar-Or et al. 2008). This suggests that memory B cells may have a role in the mechanisms underlying demyelination in RRMS. It also suggests that they might have utility as a marker for disease suppression. However, the suppression of

memory B cells by DMT, and their contribution to pathogenesis in MS, remains unclear.

The maxim that CD4 Th17 cells play an important role in RRMS pathogenesis is largely based on animal models (Rostami and Ceric 2013; Volpe, Battistini, and Borsellino 2015). However, this failed to be demonstrated in human subjects, where their suppression in clinical trials has only produced marginal benefits (Deiß et al. 2013). It is clear then that other mechanisms must play a crucial role in demyelination and relapse.

Alemtuzumab is an anti-CD52 monoclonal antibody that is one of the most clinically efficacious DMT agents, capable of inducing long-term disease suppression (Coles et al. 2012). Studies of the B cell pool have shown that, while immature B cells rapidly repopulate after therapy, CD19+/CD27+ memory B cells are significantly depleted for up to 30 months following treatment (Coles et al. 2012; Kasper et al. 2014; Thompson et al. 2010). While alemtuzumab also suppresses CD4+ and CD8+ T cells, changes in the T cell pool do not correlate with disease activity (Bar-Or et al. 2008). Cladribine is a drug originally licensed for hairy cell and B-cell chronic lymphocytic leukaemia. It has also been shown to be highly effective in suppressing disease activity in RRMS (Leist et al. 2014). One report has suggested that it preferentially depletes the CD19 B cell pool, with only modest effects on CD4 and CD8 cells (Leist et al. 2014; Rieckmann 2009). Rituximab is anti-CD20 monoclonal antibody that suppresses T cells by approximately 20-25% (Palanichamy et al. 2014). However, it also produces a sustained depletion in memory B cells that lasts for up to a year, which parallels disease activity (Palanichamy et al. 2014; Bar-Or et al. 2008).

Taken together, these studies suggest that some of the most clinical effective DMT agents MS seem to target the memory B cell pool (CD19+/CD27+), which advocates for the role of these cells in disease activity (Baker et al. 2017). However, their degree of depletion, what subsets may be implicated, and the exact mechanisms by which they might contribute to pathogenesis, remains to be explored. While the limited reports do suggest the memory B cell pool may be affected, no studies have compared alemtuzumab and cladribine directly in terms of their effect on the compartment, and whether there may be more specific effects of specific subset depletion within the compartment.

Several studies causing B cell augmentation seem to worsen disease activity in MS. Atacicept is a homodimeric fusion protein that stimulates B cell numbers, activation and antibody production (Palanichamy et al. 2014; Bar-Or et al. 2008; Gatto 2008). It was reported to precipitate CNS inflammation and progression to clinically definite MS in a trial of optic neuritis (Sergott et al. 2015) and a clinical study in MS was discontinued after worsening of disease (Sergott et al. 2015; Kappos et al. 2014). Similarly, TNF inhibitors have been shown to augment memory B cell populations in trials of rheumatoid arthritis, sometimes leading to development of CNS demyelinating disease (Roll et al. 2012; Souto-Carneiro et al. 2009). TNF inhibitors have further been shown to worsen the disease course of MS (van Oosten et al. 1997). These data provide some indirect evidence that memory B cells may have an important function the manifestation of disease in RRMS (Baker et al. 2017).

It is unclear what the precise role of memory B cells is in driving CNS inflammation, as they are a heterogeneous population with many different functions. In the progression of disease activity there is a shift in the makeup of unswitched and naïve B cells towards CD19+/CD27+ memory cells (van Oosten et al. 1997; Haas et al.

2011). It is known that they express co-stimulatory molecules and major histocompatibility (MHC) proteins and can present myelin antigens (Michel et al. 2015; Harp et al. 2010). Given this, it has been posited that they may act as important antigen presenting cells to drive T cell mediated mechanisms of inflammation (Baker, D., Marta, M., Pryce, G., Giovannoni, G., Schmierer, K. 2016). In particular, a subset of CD19+/CD27+/CD25+ memory B cells, which express the Interleukin 2A Receptor, are increased intrathecally in MS (de Andrés et al. 2014), and appear to have a regulatory function on CD4+ T cells (Kessel et al. 2012). If they play a crucial role in the pathogenic mechanisms of MS, and their activity correlates with disease activity, they might serve as a useful biomarker of disease activity in response to DMT (Baker, D., Marta, M., Pryce, G., Giovannoni, G., Schmierer, K. 2016; Komori et al. 2015). Thus, it is of great clinical interest to characterise which of these cells and their myriad subsets are most closely related to disease suppression.

Memory B cells are a heterogeneous group of lymphocytes (Michel et al. 2015). Which specific subsets are most closely related to disease activity requires greater elucidation. Important subsets include the class-switched IgD+ and non class-switched IgD- subtypes. Circulating plasmablasts, which co-express the CD19+/CD27+/CD38+ marker set, may also be of clinical importance, as their levels are increased throughout the course of MS (Michel et al. 2015; Cepok 2005). Only one study has examined a pathogenic subset of CD27+/CD38low memory B cells in MS, which are increased in untreated disease (Li et al. 2015). However, no previous study has examined the activity of memory B cell subsets in response to therapy. We would therefore like to characterise not only the general CD19+/CD27+ pool, but also subsets of IgD± and CD25± memory B cells and CD38+ plasmablasts. This may give us greater insight into the effects of DMT and the role of B cells subsets in RRMS.

Limited therapeutic evidence supports the notion that CD19+/27+ memory B cells may play a vital role in contributing to the disease pathophysiology of MS (Kasper et al. 2014) (Thompson et al. 2010; Rieckmann 2009; Palanichamy et al. 2014). Moreover, CD27 is associated with immunoglobulin index in cerebrospinal fluid in MS (Komori et al. 2015). Their association with disease activity, and suppression by effective DMT, suggests that they might play a vital role in MS pathogenesis. If CD19+/CD27+ memory B cells are proven to be key protagonists in the disease process, they might be valuable targets for the development of novel therapeutic agents that specifically target the memory B cell pool.

### 5.3 Rationale

**Study objectives:** To study the impact of cladribine on peripheral and intrathecal B-cell, plasma cells, T cells and Tregs.

While some treatments have been shown to affect this pool, it is not clear to what degree, or if there are specific pathogenic subsets that might be interesting drug targets, in order to maximise clinical efficacy while minimising adverse effects. This study will therefore attempt to explore the memory B cell pool and related subsets, plasmablasts and T cell family in order to further characterise their response to therapy.

## Hypotheses

1. Oral cladribine preferentially targets memory B cells and that the repopulation of B-cells is driven initially by immature and subsequently mature B-cells, but not memory B cells.
2. In people with MS (pwMS) the administration of cladribine will reduce CSF biomarkers of both B cell and plasma cell activity (OCBs and absolute free light chain levels) and markers of CNS inflammation (CXCL-13) and neuroaxonal damage (neurofilament light chain).
3. The administration of oral cladribine to pwMS will result in changes, or rejuvenation, of immune repertoire at both a B-cell (immunoglobulin) and T-cell (T cell receptor) level.

### 5.4 Risks / benefits

There are small risks associated with venepuncture and lumbar puncture that will form the main method of sample collection. These include haematoma formation, infection, nerve damage, haemoconcentration, extravasations, syncope and fainting, petechiae, excessive bleeding, oedema, fear and phobia, thrombosis, arterial puncture, pain and allergy (Campbell, Carrington, and Limber 1999). However, these risks are rare if performed competently. There are no direct benefits to the participants taking part in the study. However, there may be a future benefit to current or future MS patients, depending on the results of the study.

## 6. Study objectives

### 6.1 Primary objective

To quantify the temporal changes of memory B cells (CD19+/CD27+/IgD-/+), plasmablasts (CD19-/CD138+/CD38+) and T cells (CD4/CD45RA-/+; CCR7-/+; CD8+/CD45RA-/+; CCR7-/+), Tregs (CD4/CD8)/CD25+/CD127-/Fox3 P+) in the peripheral venous blood of pwMS with RRMS over 96w of treatment with oral cladribine. These will be compared to the populations of non-memory or class-switched B cells (immature/transitional B cells CD10+/CD38+/CD19+, immature regulatory B cells CD10+/CD38+/CD19+/CD24+/IL-10+, mature B cells CD10-/CD38+/CD19+).

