### 6.4 Primary endpoint

The time course of B, plasmablast and T cell depletion and re-population over 96w to see if any particular population of cells is more susceptible to cladribine, i.e. memory B-cells (CD19+/CD27+). These changes will be compared to populations of naïve B cells.

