## 8. Study design

Patients will be required to give consent for 15mL of peripheral venous blood (plasma and serum), urine and CSF to be collected at multiple time points over 96 weeks. These samples will be collected in addition to those collected for routine clinical monitoring. They will be informed that their decision to consent for their blood products to be used in research will have no impact on their current or future treatment, and it should not affect their decision to start, continue or discontinue their MS therapy.

Venous blood samples will be analysed by flow cytometry. B cell populations will be determined using specific markers for B cell populations including CD10, CD19, CD25, CD27, CD38 and IgD. This will allow the analysis of the number of memory B cells (CD19+/CD27+), memory B cell subsets (CD19+/CD27+/IgD-/+ and CD19+/CD27+/CD25-/+) and plasmablasts (CD19+/CD27+/CD38+) in the subject's blood samples. As controls, naive B cells CD19+/CD27 and T cells (CD19

/CD3+/CD4+/CD8+) will also be examined. Whole blood for DNA extraction will be collected and stored for deep sequencing to analyse the B and T cell repertoire using Adaptive Biotechnologies' immunoSEQ technology; these assays can identify millions of T- and B-cell receptors in a single sample. Using this technology will allow us to compare the impact of cladribine on the adaptive immune system over time and to compare it with similar data from alemtuzumab treated subjects from [name] laboratory in Munster.

CSF will be collected using an atraumatic needle. CSF will be processed for routine biochemistry and aliquots will be stored for OCBs, FLC, B cells: soluble CD19 and plasma cells: soluble CD138; inflammatory markers: urine neopterin and multiplex cytokine profile; and neurodegenerative markers: NF, GFAP, NCAM, GAP-43 and S100B levels.

Study subjects will also be examined annually, have a routine annual MRI T2 lesion load and gadolinium enhancement, and the following outcome measures assessed EDSS, 9-HPT, T25FW, MSIS-29 and other routine clinical outcome measures at 24 weekly intervals.

Historical control data from 12 post-alemtuzumab treated subjects (Barts Health) for secondary endpoints (CSF OCB & FLC) and tertiary endpoints (B and T cell repertoires) will be used as comparators.

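### The mature B-cell comparator in the primary objective can overlap with the memory target, and the primary endpoint names a different comparator with nothing to say which governs

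*Combined protocol and SAP*

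**What the plan says.** Section 6.1, repeated in the synopsis, sets out to follow "memory B cells (CD19+/CD27+/IgD" negative or positive) over 96 weeks, and adds: "These will be compared to the populations of non-memory or class-switched B cells". The comparators listed in brackets are immature/transitional cells, immature regulatory cells, and "mature B cells CD10-/CD38+/CD19" positive. None of the three gates carries a CD27 term.

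Section 6.4, the primary endpoint, names something else: "These changes will be compared to populations of naïve B cells". Section 8 gates that comparator and adds a second: "As controls, naive B cells CD19 + /CD27 - and T cells". T cells are also a population under test in Sections 6.1 and 6.4.

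Hypothesis 1 is that the "repopulation of B-cells is driven initially by immature and subsequently mature B-cells, but not memory B cells".

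Section 11.2 describes the kinetics by reductions relative to baseline, absolute reductions, and best-fit time to nadir and recovery. It plans an interim analysis of year 1 data, gives no gates, and defers detail to a later SAP.

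**The concern.** The primary endpoint asks whether memory B cells are more susceptible to cladribine than other B cells. The answer is a comparison of curves, so the gate definitions determine what is compared. If some memory cells also sit in the comparator gate, depletion of memory cells pulls the comparator down with them and the contrast narrows. When memory cells return, the comparator rises even if no mature naive cell has returned, and hypothesis 1 relies on telling those two apart. With two comparators in the protocol and no rule for choosing, the choice could also be made after the year 1 data have been seen.

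**Working it through.** **Step 1. Gates side by side.**

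| Population | Gate | Where | CD27 term | CD38 term | CD10 term |
|---|---|---|---|---|---|
| Memory (target) | CD19+/CD27+/IgD-/+ | Synopsis, 6.1 | + | none | none |
| Mature (comparator) | CD10-/CD38+/CD19+ | Synopsis, 6.1 | none | + | - |
| Immature/transitional (comparator) | CD10+/CD38+/CD19+ | Synopsis, 6.1 | none | + | + |
| Naive (control) | CD19+/CD27- | 8 (for 6.4) | - | none | none |
| Plasmablast | CD19+/CD27+/CD38+ | 8 | + | + | none |
| Plasmablast | CD19-/CD138+/CD38+ | Synopsis, 6.1 | none | + | none |

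**Step 2. Overlap under Section 6.1.** A CD19+/CD27+/CD38+/CD10- cell satisfies the memory gate and the mature gate. The protocol recognises cells of this kind. Section 8 plasmablasts are CD19+/CD27+/CD38+, and any that are CD10- fall in both gates. The B-cells part of Section 5.2 adds: "Only one study has examined a pathogenic subset of CD27 + /CD38 low memory B cells in MS". Whether CD38low cells count as CD38+ depends on a cut-off that is not stated. CD38-negative memory cells do not enter the mature gate.

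**Step 3. Overlap under Sections 6.4 and 8.** CD19+/CD27- and CD19+/CD27+ are disjoint by definition, so the overlap is zero. But the gate has no CD10 term and therefore pools immature with mature cells. Only the synopsis and Section 6.1 separate those two, and they do so with the overlapping mature gate.

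**Step 4. Effect on depletion.** Let s be the share of the baseline mature gate that is memory cells, and M and N the fractions of memory and non-memory cells remaining. Then

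- fraction of the gate remaining: G = sM + (1 - s)N
- observed difference: G - M = (1 - s)(N - M)

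The documents give none of s, M or N. Assume M = 10% and N = 60%, a true difference of 50 points.

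**Step 5. Effect on repopulation.** Let memory cells return from 10% to 50% of baseline while non-memory cells stay flat. The gate rises by s × (50 - 10) = 40s points.

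| s (assumed) | Observed difference (true 50) | Rise in mature gate (true 0) |
|---|---|---|
| 5% | 0.95 × 50 = 47.5 | 2 |
| 10% | 0.90 × 50 = 45 | 4 |
| 20% | 0.80 × 50 = 40 | 8 |
| 30% | 0.70 × 50 = 35 | 12 |
| 50% | 0.50 × 50 = 25 | 20 |

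With CD27- in the comparator gate, s = 0 and both effects vanish.

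**Step 6. What is not touched.** The plan states no effect size or sample size for this comparison. Its 11 subjects concern loss of CSF OCBs (50% versus 0%, 80% power, alpha 5%). A two-sided two-proportion formula without continuity correction reproduces 11, and nothing above enters it.

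**The case against.** The strongest reply is that the comparison named in the primary endpoint is clean. Section 6.4 says naive cells and Section 8 gates them CD27-, so a reader who infers that the primary endpoint's comparator contains memory cells goes further than the documents. This stands: the overlap belongs to the primary objective and the synopsis. It does not dispose of the point, because no text ranks the two comparators and the clean one cannot separate the immature and mature cells of hypothesis 1.

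A reader might also infer that class-switched cells are placed on both sides. The background section does list them as a memory subset: "Important subsets include the class-switched IgD + and non class-switched IgD- subtypes". But the comparator phrase in Section 6.1 can be read as neither memory nor class-switched, and no gate in the brackets is labelled class-switched. That half is ambiguous wording. Even on the kinder reading, nothing in the mature gate excludes CD27+ cells.

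Nor could a rising mature curve alone confirm hypothesis 1. Memory cells are counted separately, and if they returned, their own curve would rise and contradict it. This stands too. What remains at risk is the size and timing of the mature recovery.

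Finally, the study is exploratory and descriptive, so no error rate or power is affected. The relevant markers are stained together, so the data could be re-gated, and a detailed SAP is promised before data become available. These points lower the stakes and make the repair easy, but they do not supply the missing definition.

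**Conclusion.** The point holds as an unresolved contradiction between two comparators, one of which can overlap with the target population. Under the Section 6.1 gate the direction is clear: the memory versus mature contrast in relative depletion is multiplied by (1 - s), and returning CD27+/CD38+/CD10- cells inflate apparent mature repopulation.

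The size is not established. The figures in the working rest on assumed values of s, M and N, and on the further assumption that the overlapping cells fall and return in step with the whole memory pool. They apply to relative reductions and to one of the three Section 6.1 comparators. A reader should not take any row of the table as the expected loss.

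A reader might also infer from the background sentence on IgD that switched and unswitched results would be reported under each other's names. The labels there do look reversed on general immunological grounds, but Sections 6.1 and 8 gate on IgD-/+ without those names and no analysis depends on them. It is a minor background correction.

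**What to change.** Before the year 1 interim analysis, and preferably in the promised SAP, use one set of mutually exclusive gates in the synopsis and Sections 6.1, 6.4 and 8:

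- State CD27- in every non-memory B-cell comparator gate.
- Keep transitional cells (CD19+/CD27-/CD10+/CD38+) and mature naive cells (CD19+/CD27-/CD10-) separate, and say whether the mature gate keeps a CD38 requirement. The regulatory gate is the immature gate with two further markers, so report it as a nested subset.
- Separate plasmablasts from memory cells with a stated CD38 cut-off. Adding CD27- to the comparator is not enough, since a memory gate without a CD38 limit still includes Section 8 plasmablasts. Reconcile the two plasmablast definitions as well.
- Delete or clarify the reference to class-switched cells in the comparator phrase.
- State which comparator answers the susceptibility question, and whether T cells are controls or a population under test.
- Check the IgD labels in the background text.

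CD10, CD19, CD27, CD38 and IgD are all in the Section 15.3 panel, so these B-cell gates need no new reagent, sample or visit. The cost is protocol wording and a gating template. The OCB sample size does not change.
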